8.5 Death

All death records will be presented in data listings. Subject incidence of deaths within and outside of 30 days of last dose of study treatment and the cause of death will be summarized.

8.6 Vital Signs and Pulse Oximetry

Vital signs (blood pressure, heart rate, respiration rate, temperature), pulse oximetry, and weight (with percent change from baseline) will be presented in data listings.

8.7 ECOG Performance Status

ECOG performance status scores will be summarized for baseline, and worst-case shift from baseline in a table and presented in data listings.

8.8 Cardiac Assessments

Cardiac assessments including electrocardiogram (ECG) and echocardiogram (ECHO) assessment date and results along with clinical significance will be presented in data listings. For SL-172154 + PLD regimen, ECHO percent change from baseline and a flag “Low” will be displayed if a value is lower than the lower limit of normal.

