3.7.2.4 Management of Left Ventricular Ejection Fraction Decreased [PLD Cohort]

If a subject's left ventricular ejection fraction (LVEF) drops below institutional limit of normal or by at least 15% (absolute percentage points) from baseline value, study treatment (SL-172154, PLD or combination) should be discontinued. LVEF should be re-assessed within 45 days and every three months until full recovery. Upon full recovery, defined as LVEF increase to within 5% (absolute percentage points) of baseline within 45 days from LVEF nadir, study treatment (SL-172154, PLD or combination) can be resumed at investigator's discretion. Continuation of treatment should be followed by additional LVEF evaluation within 2 weeks.

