5.3.2 Baseline and Change from Baseline

Unless otherwise specified, the baseline value is defined as the last value obtained on or before the date and time of the first dose of any study drug (SL-172154, PLD or MIRV). Post-baseline values are defined as value obtained after the first dose of study drug.

Change from baseline is calculated as:

- Post-baseline value - baseline value

Percent change from baseline is calculated as:

- $(\text{Post-baseline value} - \text{baseline value}) * 100 / \text{baseline value}$

If either baseline or post-baseline value is missing, the change from baseline and percent change from baseline will be missing.

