	16.2.7.2	Dose Limiting Toxicities	DLT evaluable
	16.2.7.3	SL-172154-Related Adverse Events	All Treated
	16.2.7.4	PLD-Related Adverse Events	All Treated
	16.2.7.5	Adverse Events with Toxicity Grade 3 or 4	All Treated
	16.2.7.6	Fatal Adverse Event	All Treated
	16.2.7.7	Serious Adverse Events	All Treated
	16.2.7.8	SL-172154 Infusion Related Reaction Adverse Events	All Treated
	16.2.7.9.1	Adverse Events Leading to SL-172154 Infusion Interrupted	All Treated
	16.2.7.9.2	Adverse Events Leading to PLD Infusion Interrupted	All Treated
	16.2.7.10.1	Adverse Events Leading to SL-172154 Dose Reduced	All Treated
	16.2.7.10.2	Adverse Events Leading to PLD Dose Reduced	All Treated
	16.2.7.11.1	Adverse Events Leading to SL-172154 Dose Not Given or Delayed	All Treated
	16.2.7.11.2	Adverse Events Leading to PLD Dose Not Given or Delayed	All Treated
	16.2.7.12.1	Adverse Events Leading to SL-172154 Drug Withdrawn	All Treated
	16.2.7.12.2	Adverse Events Leading to PLD Drug Withdrawn	All Treated
	16.2.7.13	SL-172154 Infusion Related Reaction Signs and Symptoms	All Treated
	16.2.7.14	Death	All Treated
	16.2.7.15b	All MIRV-Related Grade 3 or 4 Ocular Toxicity Adverse Events	All Treated

ICH Heading	Listing Number	Listing Description	Analysis Population
	16.2.7.16	All Adverse Events for Screen Failure Population	Screen Failure
16.2.8		Individual Laboratory Measurements	
	16.2.8.1	Hematology	All Treated
	16.2.8.2	Clinical Chemistry (including ferritin and haptoglobin)	All Treated
	16.2.8.3	Coagulation and Thyroid Function	All Treated
16.2.9		Listing of other safety data	
	16.2.9.1	Vital Signs and Pulse Oximetry	All Treated
	16.2.9.2	ECOG Performance Status	All Treated
	16.2.9.3	Cardiac Assessments: ECG	All Treated
	16.2.9.4	Cardiac Assessments: ECHO	All Treated
	16.2.9.5	Blood Phenotyping and Direct Antiglobulin Test	All Treated
	16.2.9.6	Transfusions	All Treated
	16.2.9.7b	Ocular Symptom Assessment [Regimen (SL-172154 + MIRV) only]	All Treated

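### For the PLD regimen the SAP shows LVEF as relative percent change, so subjects who meet only the protocol's 15-point limb are not flagged

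*SAP*

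**What the plan says.** Protocol 3.7.2.4 applies when a PLD subject's LVEF "drops below institutional limit of normal or by at least 15% (absolute percentage points) from baseline value". The two limbs are alternatives. Full recovery is "defined as LVEF increase to within 5% (absolute percentage points) of baseline within 45 days from LVEF nadir". The drop limb and the recovery rule are therefore both expressed in absolute points. Protocol 6.5.6 schedules LVEF by ECHO or MUGA at screening, every 8 weeks on PLD and at the post-treatment visit.

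SAP 8.8 provides that "echocardiogram (ECHO) assessment date and results along with clinical significance will be presented in data listings". For the PLD regimen it adds "ECHO percent change from baseline" and a *Low* flag that "will be displayed if a value is lower than the lower limit of normal". SAP 5.3.2 fixes the scale: "Percent change from baseline is calculated as" the difference from baseline, times 100, divided by baseline. The same section also defines plain change from baseline, but 8.8 does not call for it.

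The only planned LVEF output is Listing 16.2.9.4, "Cardiac Assessments: ECHO" (SAP 13.3). The table list in SAP 13.1 contains no LVEF table.

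**The concern.** LVEF is itself a percentage, so a column headed percent change is easily read as points. The protocol's change limb is in points and the SAP's derived variable is not, so the displayed figure cannot be compared with the protocol's 15 or its 5. The one planned flag addresses the other limb. A subject can therefore meet the protocol criterion through the 15-point limb alone without anything in the planned output marking it.

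Safety is a primary objective. Protocol 1.7.1 names myocardial damage as a doxorubicin risk, with an 11% risk of cardiotoxicity as lifetime anthracycline exposure approaches 450 to 550 mg/m². SAP 8.1.3 already counts subjects above 450 mg/m² cumulative PLD, so exposure is summarised while the protocol's own LVEF change criterion is not derived. What is at stake is the completeness and readability of one safety output.

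**Working it through.** There is no sample size, power or error rate to reproduce. The check is arithmetic on the two scales.

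**Inputs**
- Drop limb: at least 15 absolute points (Protocol 3.7.2.4).
- Recovery: within 5 absolute points of baseline (Protocol 3.7.2.4).
- Relative change = (value - baseline) x 100 / baseline (SAP 5.3.2).
- *Low* flag: value below the lower limit of normal, written L (SAP 8.8).
- PLD entry: baseline LVEF above 50% (Protocol 4.1, criterion 13).
- L is not given as a number in the documents. Assumed range: 50 to 55.

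**Step 1: a 15-point fall on the SAP's scale.** Relative change = -15 x 100 / baseline. The recovery edge is -5 x 100 / baseline.

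| Baseline | Value after 15-point fall | Shown as | Points in a 15% relative fall | Recovery edge shown as |
|---|---|---|---|---|
| 51 | 36 | -29.4% | 7.65 | -9.8% |
| 55 | 40 | -27.3% | 8.25 | -9.1% |
| 60 | 45 | -25.0% | 9.00 | -8.3% |
| 65 | 50 | -23.1% | 9.75 | -7.7% |
| 70 | 55 | -21.4% | 10.50 | -7.1% |
| 75 | 60 | -20.0% | 11.25 | -6.7% |

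The same 15 points spans -29.4% to -20.0% over these baselines, so no single percent-change value reproduces the limb.

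**Step 2: the same displayed value, different status.** A fall from 75 to 60 gives -15 x 100 / 75 = -20.0%. A fall from 60 to 48 gives -12 x 100 / 60 = -20.0%. The first meets the 15-point limb and the second does not.

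**Step 3: whom the *Low* flag misses.** A subject with baseline B meets the 15-point limb when the value is at most B - 15, and escapes the flag when the value is at least L. Both are possible only if B - 15 >= L, that is B >= L + 15.
- L = 50: baseline of 65 or more.
- L = 53: baseline of 68 or more.
- L = 55: baseline of 70 or more.

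Below those baselines every fall of 15 points or more takes the value under L and is flagged. For example, 60 to 45 is flagged for any L above 45. By contrast, 70 to 55 meets the drop limb and is not flagged if L is 55 or lower.

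**Step 4: other planned outputs.** Nothing in SAP 13.1 to 13.3 derives absolute LVEF change or marks the 15-point limb.

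**The case against.** The strongest reply is that nothing is lost. Results are listed by subject, so absolute change is one subtraction, and the planned PLD regimen is only about 12 + 14 = 26 subjects. The *Low* flag already handles one limb and most 15-point falls. Protocol 3.7.2.4 is a management rule rather than an endpoint, and LVEF is not named among the outcome measures. Its consequences also appear elsewhere: Protocol 6.5.6 has treatment-emergent abnormalities of clinical consequence reported as AEs, Tables 14.3.1.19.1 and 14.3.1.19.2 cover AEs leading to withdrawal of SL-172154 and of PLD, and Listing 16.2.1.2 covers treatment discontinuation.

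Most of this stands, and it limits the point in two ways. A reader might infer that the cardiac output cannot show who met the protocol criterion. The documents do not support that, because the *Low* flag identifies one limb in full and the listed results allow the other to be worked out. A reader might also infer that the SAP applies a 15% cut-off on the relative scale and so misclassifies subjects. It does not: SAP 8.8 sets no percent-change threshold.

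The reply does not explain why the one derived LVEF variable is on a scale that the protocol does not use. Nor do the AE and discontinuation outputs mark the 15-point limb.

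**Conclusion.** The point holds in a narrow form. SAP 8.8 derives relative change where the protocol's drop and recovery limbs use absolute points, and no planned output flags the 15-point limb. The subjects affected are those who meet that limb alone, with LVEF still at or above the limit. They must be identified by hand.

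The size depends on the institutional limit. With an assumed limit of 50 to 55, only subjects with a baseline of at least 65 to 70 can fall in this group. The documents give no baseline LVEF distribution, so the number cannot be estimated. The reasoning also assumes that the lower limit of normal behind the SAP flag is the institutional limit in the protocol.

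This is a minor improvement to a safety listing. It concerns reporting only and takes no view on the clinical rule.

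**What to change.** In SAP 8.8, for the PLD regimen:
- Replace or supplement percent change with absolute change from baseline in percentage points, using the plain change already defined in SAP 5.3.2.
- Keep the *Low* flag and add a separate flag for falls of 15 points or more.
- Add n (%) of subjects meeting either limb at any post-baseline assessment.
- State that this applies to LVEF from ECHO or MUGA. The protocol allows both, while SAP 8.8 and Listing 16.2.9.4 name only ECHO.
- Reword the sentence so that change is shown at every assessment. As written, it can be read as showing percent change only when a value is below normal.

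The cost is one derived variable, one flag and one small table. No extra data collection is needed.

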8.9 Blood Phenotype and Direct Antiglobulin Test

Blood phenotype and direct antiglobulin test (DAT) assessment date and results will be presented in data listings.

8.10 Transfusion

Transfusions data will be presented in data listings.

8.11 Ocular Symptom Assessment and Ophthalmic Examination [MIRV Regimen Only]

For subjects enrolled in Regimen (SL172154 + MIRV), ocular symptom assessment and ophthalmic examination will be performed per the schedule of assessments in protocol. Relevant findings will be reported as AE data. In addition to AE tables and listings, the ocular symptom assessment results will be presented in a data listing as well.

9. PHARMACOKINETIC ANALYSES

9.1 SL-172154 PK Analyses

The merge of SL-172154 serum concentration with CRF data will be performed after database lock by Shattuck Labs to generate a dataset with actual PK sampling times, actual time relative to the start of infusion, and SL-172154 concentrations. Derivation of PK parameters will be performed by Certara using Phoenix WinNonlin (Version 8.4 or higher).

Unless otherwise specified, all PK data analyses will be based on the SL-172154 PK population and summarized for each treatment regimen.

9.1.1 Data Handling

The nominal time relative to the start of infusion will be calculated as the planned time relative to the end of infusion plus the planned infusion duration. The actual time relative to the start of infusion will be calculated as the actual sampling time relative to the start of infusion (SOI) or the SOI of the first infusion period if there is (are)with infusion interruption(s). Missing PK sampling time will be handled as the following when calculating the actual time relative to SOI:

- If a sampling time is missing and no infusion interruption, the actual time relative to SOI will be calculated as time from SOI to end of infusion (EOI) plus planned time relative EOI.
- If a sampling time is missing and there is interruption(s) during the infusion, the actual time relative to SOI will be calculated as time from the SOI of first infusion period to the EOI of the last infusion period plus planned infusion time relative to EOI.

Concentration values that are below the limit of quantification (BLQ) will be handled as the following:

- If a BLQ value occurs at the predose, the BLQ value will be assigned as zero concentration. If one or more BLQ values occur in a profile after infusion but before the first measurable concentration, the BLQ values will be assigned a value of zero

concentration. For linear plots, zero concentration value(s) will be included in the plot. For log-linear plots, zero concentration value(s) will be assigned a missing value.

- If a BLQ value occurs after a measurable concentration in a profile and is followed by a measurable concentration, then the BLQ will be set as missing.
- If a BLQ value occurs after the last measurable concentration in a profile, then the BLQ values will be set as missing.
- If two or more BLQ values occur in succession after a measurable concentration, the profile will be deemed to have terminated at the first BLQ value (BLQ values will be set to missing) and any subsequent concentration will be set as missing.
- BLQ values that are set to be missing will be omitted from PK parameter generation, concentration summary, and the individual PK profile plots.
- For the time point that all concentrations are BLQ and all BLQ results are imputed to be zero, then the mean/median concentration will be reported as zero.
- For the time point that only some concentrations are BLQ and BLQ values are imputed to be zero, the mean/median will be reported unless the mean/median value is below the LLQ (10 ng/ml), in which case the value will be assigned as BLQ.

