SL-172154 per investigator assessment were reported in 23 subjects (89%), with the most common (> 15% of subjects) being IRR, fatigue, nausea and decreased appetite. IRRs are further described in Section 1.7.1. Eleven subjects (42%) reported at least one Grade 3/4 AE. Of the Grade 3/4 AEs, anemia, aspartate aminotransferase (AST) increased, ALT increased, back pain, thrombocytopenia, IRR, muscular weakness (all in 1 subject), and lymphopenia (2 subjects) were considered to be related to SL-172154. There were 6 subjects with serious adverse events (SAEs), none of which were considered drug-related. No Grade 5 AEs have been reported and no AEs led to permanent discontinuation of SL-172154.

The PK parameters for SL-172154 have been estimated in 23 subjects receiving 0.1 mg/kg (n=3), 0.3 mg/kg (n=6), 1.0 mg/kg (n=4), 3.0 mg/kg (n=5) and 10 mg/kg (n=5) in Study SL03-OHD-101. For doses > 0.1 mg/kg that have been evaluated, serum SL-172154 concentrations were above the lower limit of quantification (LLOQ) for 2 to 25 hours after the start-of-infusion. Following a dose of \geq 1.0 mg/kg, concentrations appear to decline in a weakly biphasic manner. In general, serum SL-172154 C_{max} and AUC_{last} values increased with increasing dose, with evidence of non-linearity noted by a positive relationship between dose-normalized exposure versus the administered dose. Additionally, marked variability in C_{max} and AUC values at dose levels \geq 1.0 mg/kg was noted, which is most likely due to dosing interruption secondary to infusion-related reactions. Clearance and volume of distribution decreased as a function of dose between 1.0 mg/kg and 3.0 mg/kg. For doses \geq 0.3 mg/kg, geometric mean values indicated a short serum half-life (less than 1 hour). Preliminary evidence of decreasing clearance with increasing dose may be due to target mediated drug disposition. In general, subject serum concentrations and exposure (i.e., C_{max} , AUC) were within the same magnitude on Cycle 1, Days 1 and 15 and Cycle 2, Day 1, indicating no accumulation and no time-dependence on SL-172154 PK. Also, serum SL-172154 C_{max} and AUC_{last} values increased with increasing dose in a greater than dose proportional manner. Clearance was similar between Cycle 1, Day 15 and Cycle 2, Day 1. The volume of distribution after repeat dosing was lower than that following a single dose.

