Sections 6.1, 6.1.1, 6.2, 6.2.1 Schedules of assessments Section 6.5.9 Local and Central Clinical Laboratory Assessments Section 6.5.9.1 Ad Hoc Labs for IRR or CRS AEs	
Description of Change:
 
 Based on emerging data, removal of SL-172154 PK sample collections from C3 onwards, PTV or SFU) and updates to corresponding footnotes. 
Rationale/Justification: Analysis of serum concentrations of SL-172154 in a completed Phase I study in ovarian cancer patients (SL03-OHD-101) showed that following single and multiple IV infusions of 0.1 to 10 mg/kg SL-172154, maximum mean serum SL-172154 concentrations were reached at the end of infusion followed by multi-phasic decline and rapid clearance. SL-172154 concentrations were only detectable (>10.0 ng/mL) post-EOI for up to 2 hours for ≤1.0mg/kg and up to 8 hours for 3.0 mg/kg. Based on these data, pre-dose SL-172154 infusion PK sample collection was removed from C3 onwards as concentrations should not be detectable this long after dosing.
 
Description of Change:
 
 Addition of footnote to describe collection of ad hoc SL-172154 ADA if subject discontinues SL-172154 due to IRR but continues on PLD or MIRV. 
Rationale/Justification: If an IRR leads to discontinuation of SL-172154, patients have the option to continue on PLD or MIRV monotherapy. To investigate for the presence of antidrug antibodies to SL-172154, text was added to ensure additional ADA sample would be collected at a subsequent visit, if feasible.

Section 6.11 Assessment of Anti-Tumor Activity	
Description of Change: Removal of statement regarding scans during delay for toxicity management. to avoid confusion.

Section	Description/Rationale
	Rationale/Justification: There was a sentence about not having to repeat scans when subsequent cycles are delayed for toxicity management. This sentence was unclear, not relevant, and led to confusion. It was therefore removed.
Section 7.1.1 Events not Qualifying as AEs/SAEs	Description of Change: Clarification that deaths due to disease progression should not be reported as AE/SAEs. Rationale/Justification: For the purpose of clarification, a sentence was added to explain that deaths that are clearly determined to be due to disease progression should not be reported as AEs/SAEs.

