9.1.2 SL-172154 Concentration Measures

SL-172154 concentration values will be sorted by sample collection day, and nominal time points in the listing. All SL-172154 concentration values including BLQ will be listed in the same precision as the source data.

SL-172154 concentration will be summarized for each nominal time point relative to the EOI. Standard summary statistics will be calculated (i.e., mean, standard deviation, median, minimum, maximum, coefficient of variation (CV%), geometric mean, geometric CV%).

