	14.3.7.1	SL-172154 Serum Concentration	SL-172154 PK	Yes

ICH Heading	Table Number	Table Description	Analysis Population	aCSR
	14.3.7.2	SL-172154 PK Parameters	SL-172154 PK	Yes
	14.3.7.3b	MIRV Serum Concentration	MIRV PK	Yes
14.3.8		ADA Data		
	14.3.8.1	Treatment Induced SL-172154 Anti-Drug Antibodies	SL-172154 Immunogenicity	Yes
	14.3.8.2	SL-172154 Onset and Duration of Treatment Induced SL-172154 Anti-Drug Antibodies	SL-172154 Immunogenicity	Yes
	14.3.8.3b	Treatment Induced MIRV Anti-Drug Antibodies	MIRV Immunogenicity	Yes

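### Dropping SL-172154 BLQ values that follow a measurable concentration from the by-time-point summary biases mixed post-infusion rows upward

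*SAP*

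**What the plan says.** SAP 9.1.1 handles a BLQ value according to its position in the subject's profile.

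- **Before any measurable value.** "If a BLQ value occurs at the predose, the BLQ value will be assigned as zero concentration". BLQ results after the infusion but before the first quantifiable one are also set to zero.
- **After a measurable value.** A BLQ result between two measurable ones becomes missing. For trailing values: "If a BLQ value occurs after the last measurable concentration in a profile, then the BLQ values will be set as missing". Two or more BLQ results in a row end the profile, and anything later is also set to missing.
- **Reach of the missing rule.** "BLQ values that are set to be missing will be omitted from PK parameter generation, concentration summary, and the individual PK profile plots".
- **Row-level display rules.** If every value at a time point is BLQ and all were set to zero, the mean and median are shown as zero. The other rule begins "For the time point that only some concentrations are BLQ and BLQ values are imputed to be zero", and displays BLQ in place of a mean or median under 10 ng/mL. Both rules depend on imputation to zero.

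SAP 9.1.2 then says "SL-172154 concentration will be summarized for each nominal time point relative to the EOI". It names the mean, SD, median, minimum, maximum, CV%, geometric mean and geometric CV%, but no count of BLQ values. The output is Table 14.3.7.1, "SL-172154 Serum Concentration" (SAP 13.1), which is planned for the abbreviated report as well.

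**The concern.** A trailing BLQ result is not a missing observation: the subject was sampled and the concentration is known to be under 10 ng/mL. Leaving it out of the terminal phase of a parameter calculation is reasonable. Leaving it out of a cross-sectional summary selects subjects on the value being summarized. The row then describes only those still quantifiable, while its label suggests it describes everyone sampled.

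The plan is also inconsistent: a predose BLQ counts as zero in its row, while a BLQ result at 6 h disappears from its row. The display rule that would flag a mean under 10 ng/mL cannot act on trailing BLQ, because once those values are removed the remaining quantifiable ones average at least 10.

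At stake is how late concentrations are read in Table 14.3.7.1. The table shells are not supplied and may show n, but n alone does not separate subjects below the limit from subjects not sampled.

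**Working it through.** **Inputs.** The quantification limit is 10 ng/mL (SAP 9.1.1). Protocol 6.1.1 and 6.2.1 schedule samples up to 4 and 6 h after end of infusion (EOI), plus one at 24 h. The plan gives no figure of its own to reproduce.

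**Are mixed rows likely?** In the monotherapy study, Protocol 16.9 reports concentrations detectable "post-EOI for up to 2 hours for ≤1.0mg/kg and up to 8 hours for 3.0 mg/kg". Protocol 1.4.7, pooling doses above 0.1 mg/kg, says "serum SL-172154 concentrations were above the lower limit of quantification (LLOQ) for 2 to 25 hours after the start-of-infusion" and gives a geometric mean half-life under 1 hour. This points to mixed rows at about 4–6 h post-EOI or later at 3.0 mg/kg, and earlier at 1.0 mg/kg. The 24 h row is mixed if even one subject remains quantifiable beside others who are BLQ.

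**Direction and bounds.** Take a row with fraction q trailing BLQ and the rest quantifiable with mean mQ. Let x be the unknown mean of the BLQ values, 0 ≤ x < 10.

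- Reported mean = mQ.
- True mean = (1 − q)mQ + qx.
- Bias = q(mQ − x), which lies between q(mQ − 10) and q·mQ. It is upward because mQ ≥ 10 > x.

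| q (assumed) | mQ (assumed) | Bias, ng/mL | Reported ÷ true mean |
|---|---|---|---|
| 10% | 15 | 0.5–1.5 | 1.03–1.11 |
| 20% | 20 | 2–4 | 1.11–1.25 |
| 50% | 20 | 5–10 | 1.33–2.0 |

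**Worked row (invented values).** Ten subjects: 12, 15, 18, 22, 30 and five trailing BLQ.

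- As the SAP is written: n = 5, mean 97/5 = 19.4, median 18.0, geometric mean 18.5, minimum 12.
- Whatever the five BLQ values are, the true mean lies between 97/10 = 9.7 and (97 + 50)/10 = 14.7, so 19.4 is 1.32 to 2.0 times too high. The true median lies between (0 + 12)/2 = 6 and (10 + 12)/2 = 11.
- With half the limit (5 ng/mL) for each BLQ: n = 10, 50% BLQ, mean (97 + 25)/10 = 12.2, median 8.5, geometric mean 9.6; the last two would be shown as BLQ.
- With zero: mean 9.7 and median 6.0, both shown as BLQ; geometric mean not calculated.

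**Log-normal illustration.** The geometric mean (GM) and CV are assumptions; σ² = ln(1 + CV²), and values under 10 are treated as BLQ. Ratios are to the true mean, at CV 50/100/150%.

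| True GM | % BLQ | Current rule | Half the limit | Zero |
|---|---|---|---|---|
| 30 | 1/9/16 | 1.01/1.09/1.16 | – | – |
| 20 | 7/20/26 | 1.05/1.19/1.30 | 0.99 throughout | 0.97/0.95/0.96 |
| 10 | 50 | 1.36/1.59/1.72 | 0.91/0.97/1.00 | 0.68/0.80/0.86 |

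At 90% BLQ the current rule gives 2.09/3.27/4.22 and half the limit gives 0.95/1.25/1.43.

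**The case against.** The best counter-argument is that little depends on this. The secondary PK outcome measures are Cmax, Tmax, Cmin, AUC, half-life, clearance and volume, and dose selection draws on PK parameters, not on mean concentrations by time. Every BLQ result stays visible in Listing 16.2.5.3. This stands, and it limits the point to one descriptive table.

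Second, mixed rows are probable rather than proven. At 3.0 mg/kg the reported detection window of up to 8 h extends past the 6 h sample. The 25 h figure pools doses up to 10 mg/kg, which is not a planned level here. The 1.0 mg/kg level opens only if 3.0 mg/kg is unsafe, and no window is given for 6.0 mg/kg. This also stands. However, a window stated as an upper limit leaves room for subjects who drop below the limit sooner.

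Third, the upward direction is guaranteed only for rows of quantifiable and trailing-BLQ values. A subject with no measurable value yet in the profile enters as zero and pulls the mean down. Measurable values after two consecutive BLQ results are also removed, with uncertain effect. These cases should be uncommon and do not alter the main result.

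Fourth, substitution has its own error. That is correct, and the error is set out with the fix.

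**Conclusion.** The concern holds. SAP 9.1.1 explicitly extends the omission to the concentration summary, and neither row-level rule reaches trailing BLQ. In a row of quantifiable and trailing-BLQ subjects the reported mean is too high by q(mQ − 10) to q·mQ ng/mL; the geometric mean and minimum are also too high, and the median cannot be too low. This direction follows from the rule alone.

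The size in this trial cannot be determined. Under the assumed scenarios with up to half the row BLQ, it runs from about 1% to a factor of two, and it grows as more of the row falls below the limit. Whether mixed rows occur rests on monotherapy data that make them likely at the later sampling times. The point should be corrected, but nothing beyond Table 14.3.7.1 depends on it.

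**What to change.** Amend SAP 9.1.1 and 9.1.2 as follows.

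1. Apply set-to-missing only to parameter derivation and the individual plots.
2. In the concentration summary, keep predose and pre-first-measurable BLQ at zero as now. Retain post-dose trailing and embedded BLQ under one prespecified convention: half the limit (5 ng/mL), or the SAP's existing zero.
3. Calculate no geometric statistics in a row containing a zero. Treat BLQ values as below the limit for the median and minimum.
4. In post-dose rows, show BLQ for any mean, median or geometric mean under 10 ng/mL.
5. Report n and number (%) BLQ at every time point. This matters most, because it makes the table interpretable under any convention.

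The cost is SAP wording, one programming branch and one added row in Table 14.3.7.1. Late means will be lower, and some cells will read BLQ or not calculated.

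Neither convention is exact. Half the limit can miss the row mean by up to 5q ng/mL either way. Zero is low by up to 10q ng/mL and loses the geometric statistics. The worst error with half the limit is smaller than the least possible current bias only if 5q < q(mQ − 10), that is mQ above 15 ng/mL; for zero the condition is mQ above 20 ng/mL. Where quantifiable values sit just above the limit and BLQ values just below it, substitution may be no closer than omission, and there the BLQ count carries the information.
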